1.2 Study Drug Background and Associated Known Toxicities

Acalabrutinib is a twice daily, oral, highly selective, irreversible small-molecule inhibitor of BTK, a key component of B-cell receptor signaling (7, 8). BTK is also essential for FcεRI signaling and triggering of mast cells and basophils, the primary cells activated during anaphylaxis (9, 10). Acalabrutinib is currently FDA approved for the treatment of Mantle Cell Lymphoma (MCL).

Pharmacokinetic studies demonstrated the average bioavailability of acalabrutinib was 25%. Median time to peak acalabrutinib plasma concentrations (Tmax) was 0.75 hours. Following a single oral dose of 100 mg acalabrutinib, the median terminal elimination half-life ($t_{1/2}$) of acalabrutinib was 0.9 hours (range: 0.6 to 2.8). The t_{1/2} of the active metabolite, ACP-5862, was 6.9 hours. Acalabrutinib is predominantly metabolized in the liver by CYP3A enzymes, and to a minor extent, by glutathione conjugation and amide hydrolysis, based on in vitro studies. Following administration of a single 100 mg radiolabeled acalabrutinib dose in healthy subjects. 84% of the dose was recovered in the feces and 12% of the dose was recovered in the urine, with less than 1% of the dose excreted as unchanged acalabrutinib.

In healthy volunteers, co-administration with CYP3A inhibitors increased Cmax, and therefore the drug will not be concomitantly administered with strong or moderate inhibitors of CYP3A. Among 1029 pooled patients from clinical trials (820 patients taking acalabrutinib monotherapy across 6 trials and 209 patients taking acalabrutinib plus obinutuzumab across 2 trials), most of whom (88%) were exposed to acalabrutinib for at least 6 months, adverse reactions in ≥30% of patients included anemia, neutropenia, upper respiratory tract infection, thrombocytopenia, headache, diarrhea, and musculoskeletal pain. Acalabrutinib is also pregnancy category D.

Notably, our prior work using ibrutinib (which may have a less favorable safety profile) in adults with food allergy demonstrated no toxicity or adverse effects from up to 7 days of treatment (11), suggesting that adverse effects from BTK inhibitors may be mitigated with short-term use rather than chronic treatment.

1.3 Rationale

There are currently no treatments for food allergy. IgE uniquely arms mast cells and basophils via their surface expression of FcεRI, and when cross-linked by allergens, causes mediator release that then results in an allergic reaction. Crosslinking of the receptor is known to activate a number of kinases. BTK is a key component of FcɛRI signaling and activation of mast cells and

basophils. Since signaling mediated by FcɛRl aggregation is thought to require the activity of BTK (8.9), [name] et. al. was the first to test ibrutinib, a first generation BTK inhibitor, for its ability to prevent FcɛRI activation of human basophils in vitro (9). Ibrutinib inhibited IqE-mediated CD63, CD203c and CD11b upregulation, and release of histamine, LTC4 and IL-4 as well as the cytosolic calcium response (IC₉₀ of ≈50 nM). Ibrutinib did not inhibit basophil activation by fMLP or C5a and did not inhibit IL-13 release induced by IL-3, suggesting that BTK is required for IgEmediated activation, but not IqE-independent activation, of human basophils (12). We recently completed an open label trial to test the hypothesis that ibrutinib would abrogate IqE-mediated BAT and food SPT responses in peanut and tree nut allergic adults (11). We found that 2 doses of ibrutinib significantly reduced SPT wheal and flare area (77 and 86% reductions, respectively; overall, 44% of SPTs became negative). Additional doses up to 7 days did not demonstrate further suppression compared to 2 days. Anti-IgE induced BAT became negative in all subjects after 2 doses and remained negative during treatment. The vast majority of SPTs and BAT returned to baseline within 1 week of cessation of ibrutinib. No toxicity from treatment was observed, and ibrutinib was well-tolerated by subjects.

We now propose to extend these promising findings in a subsequent open label study using acalabrutinib, a second generation BTK inhibitor, to investigate its ability to prevent clinical allergic reactions to oral food challenge. Because acalabrutinib is more selective for BTK with fewer off-target effects, it has a more favorable safety profile (13).

Peanut and tree nut allergies are among the most common adult food allergens, and ingestion reactions can often be the most severe and are the most likely to be life-threatening (1). Additionally, peanut and tree nut allergies are usually life-long. Young adults and adolescents have a higher rate of accidental exposure and mortality as a result of food allergies than younger children, so there is an unmet need for therapies directed at food allergy, especially in this population (14). Therefore, we have chosen peanut and tree nut allergies in an effort to investigate a treatment that has the potential to benefit the most individuals with a potentially severe allergy.

2.0 STUDY OBJECTIVES

2.1 **Primary Objective**

2.1.1 To determine if short term administration of acalabrutinib to adults with peanut or tree nut allergy will reduce allergen skin test reactions and raise oral challenge thresholds

2.2 **Secondary Objectives**

- 2.2.1 To describe frequency and severity of the adverse events associated with acalabrutinib when administered in a short course of 2 days
- 2.2.2 To determine if 2 days of acalabrutinib have any impact on blood levels of total and food-specific IqE, and numbers of circulating eosinophils and basophils.

2.3 **Endpoints**

Primary Objective 2.1.1: The highest dose of food allergen that is tolerated (i.e. does not cause an objective clinical reaction) during a SBPCFC both before and while taking acalabrutinib, as defined by objective clinical findings on physical exam before/after each dose of food ingested using a published graded scoring system (15). Secondary endpoints include change in severity of clinical reaction as defined above SPT wheal size as defined by a decrease in wheal and/or flare diameter of skin prick tests to peanut/tree

2022

nut extracts, and percent activation of basophils from BAT as assessed by the percent of basophils with CD63 surface upregulation by flow cytometry.

Version: February 9,

Secondary Objective 2.2.1: Adverse events, including bleeding, cytopenias, hepatotoxicity, and renal toxicity will be monitored using laboratory testing and clinical exam as outlined in Section 4.2.

Secondary Objective 2.2.2: Change in blood levels of total and food-specific IgE, and numbers of circulating eosinophils and basophils as assessed by laboratory testing of peripheral blood samples.

Exploratory Objective: Peripheral blood will be analyzed for mast cell and basophil microparticles before, during, and after SBPCFC.

SUBJECT ELIGIBILITY 3.0

Subjects must meet all of the inclusion and exclusion criteria to be enrolled in the study. Study procedures may not begin until a subject has signed the informed consent form.

3.1 **Inclusion Criteria**

- 3.1.1 History of IgE-mediated food allergy to peanut or tree nut.
- 3.1.2 Male or female age ≥ 18 years.
- 3.1.3 Positive skin prick test to the trigger food(s), either peanut and/or tree nut(s).
- 3.1.4 Objective clinical reaction to 1,044 mg or less of the food allergen during baseline oral food challenge
- 3.1.5 Adequate organ and marrow function as defined below:

- leukocytes ≥ 3.000/mcL - absolute neutrophil count ≥ 1,500/mcL - hemoglobin ≥ 10 g/dL - platelets ≥ 100.000/mcl

within normal institutional limits - total bilirubin - AST(SGOT)/ALT(SPGT) within normal institutional limits - Creatinine within normal institutional limits

- 3.1.6 Women of child bearing potential must agree to two forms of highly effective contraception (hormonal, device, or barrier method of birth control; abstinence) prior to study entry, for the duration of study participation, and for 7 days following completion of acalabrutinib therapy. Should a woman become pregnant or suspect she is pregnant while participating in this study, she should inform the Principal Investigator and her treating physician immediately.
 - 3.1.5.1 A female of child bearing potential is any woman (regardless of sexual orientation, having undergone a tubal ligation, or remaining celibate by choice) who meets the following criteria:
 - Has not undergone a hysterectomy or bilateral oophorectomy; or
 - Has not been naturally postmenopausal for at least 12 consecutive months (i.e., has had menses at any time in the preceding 12 consecutive months).
- 3.1.7 Ability to understand and the willingness to sign a written informed consent.

Ability to clearly understand and speak English at an 8th grade reading level. For 3.1.8 safety reasons, subjects must speak English due to the anticipated need for clear and timely communication with investigators and the study team in emergency situations, since the investigators and study team are English speaking.

3.2 **Exclusion Criteria**

- 3.2.1 Subjects who have been on immunomodulatory therapies or oral corticosteroids within 1 month prior to study participation will be excluded, and those taking antihistamines must stop these drugs for one week prior to enrollment and must refrain from taking antihistamines during the duration of the study so as not to interfere with SPT responses or clinical responses during SBPCFC.
- 3.2.2 Subjects with symptoms consistent with food reactions other than type 1 hypersensitivity (such as atopic dermatitis, eosinophilic esophagitis and any other non-IgE-mediated food sensitivities) will be excluded.
- 3.2.3 History of allergic reactions to study drug or reactions attributed to compounds of similar chemical or biologic composition to acalabrutinib, including active product or excipients.
- 3.2.4 Clinically significant cardiovascular disease such as symptomatic arrhythmias, congestive heart failure, or myocardial infarction within 6 months of screening, or any Class 3 or 4 cardiac disease as defined by the New York Heart Association Functional Classification.
- 3.2.5 Psychiatric illness/social situations that would limit compliance with study requirements.
 - Subjects must not be pregnant or nursing due to the potential for congenital 3.2.6 abnormalities and the potential of this regimen to harm nursing infants.
- 3.2.7 Subjects requiring or receiving vitamin K antagonists, those with active bleeding, and those with history of bleeding disorder (e.g. Von Willebrand's disease) or prothrombin time (PT)/INR or aPTT (in the absence of lupus anticoagulant) >2x upper limit of normal.
 - Subjects with history of idiopathic urticaria, dermatographism, idiopathic or 3.2.8 unexplained anaphylaxis, or anaphylaxis (to foods or otherwise) resulting in intubation, prolonged hypotension, or neurological sequelae
- 3.2.9 Requires treatment with a strong cytochrome P450 3A4 (CYP3A4) inhibitor/inducer.or proton pump inhibitor. Note: Subjects receiving proton pump inhibitors who switch to H2receptor antagonists or antacids are eligible for enrollment to this study.
- 3.2.10 Subjects found to have active or latent Hepatitis B or C infection based on laboratory testing. Subjects who are hepatitis B core antibody (anti-HBc) positive and who are hepatitis B surface antigen (HBsAg) negative will need to have a negative polymerase chain reaction (PCR) and must be willing to undergo DNA PCR testing during the study to be eligible. Those who are HBsAg positive or hepatitis B PCR positive will be excluded. Subjects who are hepatitis C antibody positive will need to have a negative PCR result to be eligible. Those who are hepatitis C PCR positive will be excluded.
- 3.2.11 Known history of infection with HIV or any active significant infection (eg, bacterial, viral, or fungal).
- 3.2.12 Major surgical procedure within 28 days of first dose of study drug. Note: If a subject had major surgery, they must have recovered adequately from any toxicity and/or

complications from the intervention before the first dose of study drug.

- History of significant cerebrovascular disease/event, including stroke or intracranial hemorrhage, within 6 months before the first dose of study drug.
- 3.2.14 Presence of a gastrointestinal ulcer diagnosed by endoscopy within 3 months before
- 3.2.15 Uncontrolled AIHA (autoimmune hemolytic anemia) or ITP (idiopathic thrombocytopenic purpura).
- 3.2.16 Prior malignancy (or any other malignancy requiring active treatment), except for adequately treated basal cell or squamous cell skin cancer, in situ cervical cancer.
- 3.2.17 Has diffculty with or is unable to swallow oral medication, or has significant gastrointestinal disease that would limit absorption of oral medication.
- 3.2.18 Concurrent participation in another therapeutic clinical trial.

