At Visit 1, after undergoing informed consent, subjects will undergo procedures for assessment of baseline status and eligibility (clinical history and skin prick test ISPT) to peanut and/or tree nuts as well as histamine and saline SPT positive and negative controls, respectively). After eligibility is confirmed, subjects will undergo a single-blind, placebo-controlled graded food challenge (SBPCFC) of up to 4 g of peanut or tree nut protein, administered over escalating doses while being monitored in a clinical research unit (CRU) setting. Prior to the SBPCFC, 30 mL of peripheral blood will be collected for basophil activation testing (BAT), serum specific IqE to peanut/tree nuts and components, as well as toxicity lab testing monitoring. During the food challenge, subjects will be assessed for signs and symptoms of foodinduced anaphylaxis between each dose per food challenge protocol, upon report of any symptoms and should any objective change in clinical status occur. Once a confirmed reaction occurs, the food challenge will be terminated and the reaction treated until it has resolved. Subjects will be discharged from the CRU no sooner than 2 hours after completion of the food challenge. They may be observed longer should a reaction occur at the investigator's discretion. Additional blood will be drawn at fixed intervals for biomarkers of anaphylaxis including mast cell and basophil microparticle analysis. This visit will establish each subject's baseline threshold dose for peanut/tree nut reactivity.

After a minimum of a two-week recovery period, subjects will be given acalabrutinib (four doses of 100 mg of acalabrutinib to be taken orally twice daily) and return for Visit 2 to undergo repeat SPT, SBPCFC, and phlebotomy in an identical manner to Visit 1 to establish each subject's new threshold dose for peanut/tree nut reactivity while on acalabrutinib, which we hypothesize will be higher. At this point of the protocol, acalabrutinib dosing will be stopped. Follow up visits for up to 6 months after cessation of acalabrutinib will be conducted to repeat toxicity labs and skin testing.

At each visit, subjects will be monitored for toxicities, including CBC w/diff, CMP, and pregnancy testing. Prior to drug initiation and at the end of the trial, an EKG will be performed.

STUDY SUMMARY

Title	Preventing Life-Threatening Allergic Reactions with Acalabrutinib, an FDA-Approved BTK Inhibitor			
Protocol Number	MD12042018			
Phase	Phase 2			

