	Screening / Day 0	Day 2	Follow up (30 days after Visit 2)
Informed Consent	Х		
Skin prick testing	Х	X	Х
Basophil activation test	Х	Х	Х
SBPC food challenge	Х	Х	
History and PE	Х	Х	Х
Toxicity (include DLT) Evaluations	Х	X	Х
CBC	Х	Х	Х
CMP	Х	Х	Х
EKG	Х	Х	
Urine pregnancy test ^b	Х	Х	Х
Microparticle analysis	Х	Х	Х

^b Females of child-bearing potential only

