10.0 STATISTICAL CONSIDERATIONS

As this is an open label study, each patient's responsiveness will be examined compared to themselves prior to initiation of treatment.

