10.2 Sample Size and Accrual

10 subjects allows for 80% power to detect a 3-fold increase (1.1 natural log units; i.e. 1 food dose escalation) in the threshold food dose assuming that difference in threshold from post to pre is normally distributed with a standard deviation of 1.1 natural log units using a paired t test with p<0.05 as an approximation (though non-parametric tests will be utilized in the final analysis if needed). Patients will be recruited from the allergy clinics at Johns Hopkins University with a diagnosis of peanut (or tree nut) allergy by a boardcertified allergist-immunologist.

10.3 **Data Analysis**

As this is an open label trial, descriptive statistics will be used. If appropriate, the primary outcome variable of threshold dose will be log transformed, and a paired t test will be used. If assumptions for paired t test are violated, a Wilcoxon non-parametric sign test will be used. Each patient will be compared to him/herself prior to beginning treatment and at each time point in the study to assess SPT size, BAT response, and food challenge dose threshold and response. Similar methodologies will be used for analysis of adverse events.

STUDY MANAGEMENT 11.0

11.1 **Conflict of Interest**

Any investigator who has a conflict of interest with this study (patent ownership, royalties, or financial gain greater than the minimum allowable by their institution, etc.) must have the conflict reviewed Johns Hopkins University. All investigators will follow the University conflict of interest policy.

Institutional Review Board (IRB) Approval and Consent 11.2

It is expected that the IRB will have the proper representation and function in accordance with federally mandated regulations. The IRB should approve the consent form and protocol.

In obtaining and documenting informed consent, the investigator should comply with the applicable regulatory requirement(s), and should adhere to Good Clinical Practice (GCP) and to ethical principles that have their origin in the Declaration of Helsinki.

participate in the study by signing an IRB-approved consent form.

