Appendix 1: Pill Diary

		монтн				
Sunday	Monday	Tuesday	Wednesday	Thursday	Friday	Saturday
Н	4					
-						L
		L				L

The study coordinator will fill in the month and days.

Please document number of pills and time you took the ibrutinib.

STATISTICAL ANALYSIS PLAN

Study Design and Endpoints

This is an open label study of acalabrutinib in 10 food-allergic adults to determine the effect of pretreatment (100 mg twice daily for 4 doses total) with acalabrutinib on food allergen reactivity in foodallergic subjects. There are 3 planned study visits where endpoint assessments will be collected. The primary endpoint will be assessed at Visit 1 (baseline) and Visit 2 (after acalabrutinib). Secondary and exploratory endpoints will be assessed at Visits 1, 2, and 3 (follow-up).

Primary endpoint: Change in subjects' threshold dose of peanut protein to elicit an objective clinical reaction

Secondary endpoints:

- 1. Change in size of skin prick test wheal
- 2. Change in percent of ex vivo basophil activation to anti-IgE and peanut, as determined by CD63 expression

Safety considerations and toxicity monitoring: Laboratory testing (complete blood counts, serum chemistries) and electrocardiogram

Given the nature of the study, it will be stopped if >50% of patients have a DLT as described in the protocol.

Sample Size and Power Analysis

Sample size was calculated based on the primary endpoint, assuming that the difference in threshold from baseline to after acalabrutinib is normally distributed with a standard deviation of 1.1 natural log units. Therefore, 10 subjects allows for 80% power to detect a 3-fold increase (1.1 natural log units; i.e. 1 food dose escalation) in the threshold food dose, using a paired t test with p<0.05 as an approximation. though non-parametric tests will be utilized in the final analysis if needed.

Data Analysis

As this is an open label trial, each subject's responsiveness will be examined compared to themselves (at baseline) prior to initiation of treatment. Descriptive statistics will be used to analyze endpoints. The primary endpoint will be analyzed by log transformation and paired t test with p value < 0.05, if appropriate. If assumptions for paired t test are violated, a Wilcoxon non-parametric sign test will be used.

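### The challenge that selects subjects at 1,044 mg or less is also the only baseline value, so the paired test is biased toward the drug by an amount the documents do not fix

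*Combined protocol and SAP*

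**What the plan says.** Criterion 3.1.4 of the protocol makes entry depend on "Objective clinical reaction to 1,044 mg or less of the food allergen during baseline oral food challenge". The Study Schema says of the Visit 1 challenge: "This visit will establish each subject's baseline threshold dose for peanut/tree nut reactivity". The same section describes a "graded food challenge (SBPCFC) of up to 4 g of peanut or tree nut protein", and Visit 2 repeats it in the same manner, so Visit 2 can record thresholds well above the entry cap.

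The SAP (Study Design and Endpoints) measures the primary endpoint at Visits 1 and 2 only. In the Time and Events table (Section 5.4) the row "SBPC food challenge" is marked for those two visits and blank for Visit 3. The follow-up list in Section 5.3 contains no challenge.

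There is no concurrent control: in Section 10.0 "each patient's responsiveness will be examined compared to themselves prior to initiation of treatment". The placebo in the challenge (Section 5.2.1) is a same-day food placebo, not a drug placebo. Protocol Section 10.3 and the SAP (Data Analysis) plan descriptive statistics and a paired t test on the log threshold, with a Wilcoxon or sign test if its assumptions fail. Neither mentions regression to the mean, truncation, test-retest variability or a sensitivity analysis.

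**The concern.** A measured threshold is a person's underlying threshold plus error from that day's challenge. People who happened to react low at Visit 1 pass 3.1.4, and people with the same underlying threshold who happened to react high fail it. Those admitted therefore have, on average, Visit 1 readings below their own underlying level. Their expected Visit 2 reading is higher with no drug at all, and Visit 2 has room to show it.

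The paired tests take the no-drug change to be zero. With no control and no off-drug repeat, a modest rise or a borderline p value could be drug, selection or both, and the plan has no analysis that helps to tell them apart. The expected error always runs in the drug's favour.

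**Working it through.** **The plan's own figure.** Protocol Section 10.2 and the SAP give n = 10, a difference of 1.1 and an SD of the difference of 1.1 natural log units, with p < 0.05. The standardised effect is 1.1/1.1 = 1.0, and the exact two-sided paired t test has 80.3% power. The stated 80% reproduces. The issue is the null value of zero change, not this calculation.

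**Model with no drug effect.** Let X1 = T + e1 and X2 = T + e2 be the log thresholds at Visits 1 and 2. T has between-person SD sb around the log of the candidate median, and e1 and e2 are independent errors with SD sw. Entry requires X1 ≤ ln(1,044) = 6.951. Then

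expected drift = (sw²/sx) × φ(a)/Φ(a), where sx² = sb² + sw² and a = (6.951 − ln median)/sx.

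**Inputs.** The cap, n and the SD of 1.1 come from the documents. The candidate median, sb and sw do not, so they are assumed over ranges. If all of the 1.1 were test-retest noise, sw = 1.1/√2 = 0.778. That is an upper value, because the 1.1 describes an off-drug to on-drug difference and may include variation in drug response. The value 0.4 is an assumed lower case.

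**Worked case, high end.** Median 1,000 mg, sb = 1.0, sw = 0.778:
- sx = √(1 + 0.605) = 1.267 and a = (6.951 − 6.908)/1.267 = 0.034.
- φ/Φ = 0.3987/0.5136 = 0.776.
- Drift = (0.605/1.267) × 0.776 = 0.371, which is 1.45-fold.

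**Worked case, milder.** Median 300 mg, sb = 1.5, sw = 0.4:
- sx = 1.552 and a = (6.951 − 5.704)/1.552 = 0.803.
- φ/Φ = 0.2889/0.7891 = 0.366.
- Drift = (0.16/1.552) × 0.366 = 0.038, which is 1.04-fold.

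**Range over sb = 1.0 to 2.0.** Drift is from the formula. Favourable-tail error is from simulated trials of 10 with Visit 2 capped at 4 g, analysed by the planned t test (nominal 2.5%; repeat runs differ by about 0.1 point at the low end).

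| Assumed median | sw = 0.4: drift; error | sw = 0.78: drift; error | Screened out by 3.1.4 (sw = 0.78) |
|---|---|---|---|
| 100 mg | 1.01–1.02; 2.6–3.2% | 1.04–1.07; 3.0–3.8% | 3–14% |
| 300 mg | 1.04; 3.7–3.8% | 1.14–1.15; 5.3–5.6% | 16–28% |
| 1,000 mg | 1.06–1.12; 5.0–8.5% | 1.25–1.45; 8.4–17.4% | about 49% |

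The 4 g ceiling barely matters: in the high-end case it lowers 1.45 to 1.43. At a median near 30 mg the drift is negligible. As a stress case outside the range, a median of 2,000 mg with sw = 0.78 and no ceiling gives 1.32- to 1.74-fold and 11% to 33%, but with 62% to 70% of candidates screened out.

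**Check on the cause.** When the baseline value in the simulation came from an untreated challenge not used for selection, the drift was 0.00 and the two-sided error 0.047 to 0.054 in every scenario. Selection on the baseline reading is the source.

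**Scale.** With n = 10 and SD 1.1, significance needs a mean change of 2.262 × 1.1/√10 = 0.79, or 2.2-fold. The largest drift in the table, 0.371, is about a third of the planned 1.1 (0.371/1.1 = 0.34).

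**The case against.** The strongest reply is about size. The documents give no candidate threshold distribution, screen-failure share or test-retest SD, so every figure for the drift depends on assumed inputs. The 17% is a corner case: it needs a median near 1,000 mg, the smallest between-person SD and the largest within-person SD together, with about half of candidates screened out. At medians of 100 to 300 mg and sw = 0.4 the drift is 1.01- to 1.04-fold. If the drug raises thresholds 3-fold as planned, simulated power after subtracting the true drift stays at about 80% to 85%. All of this stands, and it limits the point to modest or borderline results.

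A second reply is that the paired p value is not the only evidence. That is also right. The primary objective names skin tests as well, and the Time and Events table marks skin prick and basophil activation tests before, on and after drug (the Visit 2 list in Section 5.2.2 omits the basophil test). Entry requires a positive skin test (3.1.3) and sets no limit on basophil activation. These markers support a drug effect, but they do not separate drift in the challenge threshold.

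A third reply is that the Study Schema places the challenge after eligibility is confirmed, so the challenge would not select. Criterion 3.1.4 cannot be checked without it, and no second untreated challenge is described.

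In the other direction, a reader might infer that a significant result would be an artefact, that the sample size is wrong, or that only a control arm could help. The documents support none of these. The drift stays below 3-fold in every scenario tried, and the 80% reproduces on its own inputs. A partial correction can be made from Visit 1 and Visit 2 data.

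**Conclusion.** The concern holds as a one-directional bias of unknown size. The same challenge selects subjects and supplies their baseline, so with any within-person variability the expected no-drug change is above zero, and both the paired t test and its fallback are biased toward the drug. Only the t test was simulated; the fallback shares the zero-change null.

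The range of about 1.01- to 1.45-fold, with favourable-tail error of about 2.6% to 17%, rests on the assumed medians and SDs and on normal, independent errors on the log scale. The drift is an expectation, not a certainty in ten people. A shift near the planned 3-fold would largely survive it; a small shift or a p value just under 0.05 might not. The documents also leave open whether 1,044 mg is a single or cumulative dose, and whether the endpoint is the highest tolerated or the reacting dose. Neither changes the conclusion. This is a cheap improvement, not a fatal flaw.

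**What to change.** 1. Keep and report the Visit 1 threshold of everyone challenged, including the number who fail 3.1.4. The share above the cap largely determines how big the drift can be.
2. Pre-specify one sensitivity analysis beside the paired test. Regress the Visit 2 on the Visit 1 log threshold, with Visit 2 censored at 4 g, and evaluate the change at the mean of all Visit 1 challenges (right-censored where no reaction occurred). Selection on Visit 1 does not distort this regression, and in simulation the no-drug estimate came to about zero. Express the cap, the censoring point and the endpoint on the same dose scale.
3. Tabulate the expected drift over a stated range of test-retest SDs, for example 0.4 to 0.78. The trial cannot estimate this SD, because its pairs mix test-retest noise with variation in drug response.
4. State regression to the mean as a limitation and read a modest or borderline shift in that light. Do not make attribution to the drug a pass/fail rule: the answer would depend on an SD that nobody has measured.

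The cost is one extra analysis, with no added subjects, visits or challenges. The adjusted estimate is less precise (standard error up to about 1.8 times larger in simulation), assumes that the drug effect does not depend on the true threshold, and may be slightly less favourable. A concurrent control would remove the bias at source, but would need about 17 per arm for 80% power at a difference and SD of 1.1. Splitting the planned 10 as 5 per arm gives about 29%.
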